10.1 CRF data management

The investigators should record the data in the case report form in an accurate, complete, clear and timely manner according to the original observation records of subjects.

The clinical research associate (CRA) should monitor the trial according to the trial protocol. And confirm that all CRFs are filled correctly and completely and are consistent with the original data. If there are any errors and omissions, the investigators should correct them in time. For any modifications, the original records should be clearly visible, and the corrections should be signed and dated by the investigator.

After inspection by the CRA, the CRFs should be checked and signed by the CRA, and submitted to the clinical trial data manager in time. For the transmission of the completed CRFs among investigators, CRA and data managers, there should be special records. The records should have corresponding signatures when receive and be kept properly.

The data manager should check again after data entry, and inform the CRA in time if any problems are found, and ask the investigators to answer them. All kinds of questions and answers between them should be exchanged in the form of question table, which should be kept for future reference.

10.2 Data entry and management

Before data entry, the data manager should understand the content and coding of each item in the observation form, and record the coding process in the code book for preservation. The database should be named in a standardized, easy-to-read, easy-to-find, correct, safe and confidential manner.

Data should be inputted twice using the EpiData 3.02 database system by two data entry clerks. If any problems or unforeseen circumstances are found in the process of data entry, they should be recorded well and reported in time so as to be handled quickly. After the end of data entry, partial observation forms should be checked randomly to evaluate the input quality, analyze and deal with the existing problems.

The data manager and the principal investigator should develop a data range check and logical check together based on the range and correlation of the values of various indicators in the CRF. And they should also write the corresponding computer programs to control incorrect data entry before entry, and find out the cause and correct. All errors and corrections should be recorded and properly kept.

The original CRFs should be archived and stored in order of the subject codes after completion of data entry and review, and the retrieval catalog should be filled in for review later on. Electronic data files, including databases, checking program, analysis program, analysis results, code books and supporting papers, should be classified and properly archived in multiple backups on different disks or record media to prevent damage. All original files should be archived in accordance with the prescribed time limit in the Good Clinical Practice of China.

11. Statistical analysis

11.1 Data analysis set

Full analysis set (FAS): includes those who were administrated at least one dose of camrelizumab. When a primary efficacy indicator is missing, the previous result should be carried forward according to the principle of an intention to treat analysis. The missing values of comparability analysis and secondary efficacy indicators should not be subjected to data-carry-forward, and should be analyzed based on the actual data.

Per protocol set (PPS): includes subjects who meet the inclusion criteria, do not meet the exclusion criteria and have completed the treatment regimen, that is, those who meet the trial protocol, have good compliance and have filled all required sections of the CRF are included in the PPS analysis. In this trial, subjects who drop out after half of the treatment course due to aggravation should be included as invalid subjects in the PPS analysis.

Safety set (SS): subjects who have received at least one treatment and have actual safety assessment data. The missing safety data should not be subjected to data-carry-forward; some rejected subjects who are evaluable can be included, such as those with ages beyond the inclusion criteria, but excluding those who cannot be evaluated for safety due to the use of prohibited drugs. The number of subjects in the SS will be used as the denominator for the incidence of ARs.

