Discontinuation criteria:	
Trial discontinuation means the clinical trial is not completed according to protocol and is prematurely discontinued. The main purpose of trial discontinuation is to protect the rights and interests of the subjects, ensure the quality of the trial, and avoid unnecessary economic losses.
 
(1) If serious safety issues occur during the trial, the trial should be discontinued in time;
 
(2) During the trial, major errors are found in the clinical trial protocol that make evaluation of drug efficacy difficult; or major deviations from the well-designed protocol are found in the implementation that make evaluation of drug efficacy difficult if the trial is to be continued;
 
(3) The sponsor requests to discontinue the trial (because of economic or management factors or others);
 
(4) The administrative department in charge rescinds the trial.

Dose design and treatment regimen:	
Patients will receive local rectal short-course radiotherapy. Radiotherapy will employ conformal or intensity-modulated radiation therapy, with a pelvic irradiation dose of 25 Gy/5 Fractions/1 week. Then rest for 1 week after radiotherapy and begin to receive neoadjuvant chemotherapy CAPOX and PD1 inhibitor for immunotherapy, for 2 cycles. One week after the completion of neoadjuvant therapy, a second evaluation on the primary lesions will be performed, and the surgical method is total mesorectal excision. Postoperative adjuvant therapy will be started 3-4 weeks after surgery, and the treatment regimen will be determined by the investigator. The efficacy of neoadjuvant therapy on postoperative specimens will be evaluated in accordance with Rectal Cancer Regression Grade. Treatment-related toxic and side effects will be evaluated as per CTCAE 5.0 toxic and side effects evaluation criteria.

Statistical method:	
This study will employ SPSS 16.0 statistical software package for analysis. EFS and OS will be analyzed using the Kaplan-Meier method and log-rank test.

Trial schedule:	
Estimated start time of the trial: Oct. 2019
 
Estimated time of enrollment completion: Oct. 2021
 
Estimated end time of the trial: Dec. 2025

Version No.:	V2.0

Clinical Study Protocol

Version No.: V2.0

List of Abbreviations

Abbreviations and statistics descriptions (English)

dMMR	Deficient mismatch repair protein
MSI	Microsatellite instability
mCRC	Metastatic Colorectal Cancer
PD-1	Programmed cell death protein 1

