4.4 Drop-out (withdrawal) criteria

(1) Adverse events; (2) lack of efficacy; (3) trial protocol deviation (including poor compliance); (4) trial discontinuation is determined to be necessary for subjects by the investigator due to medical concerns; (5) the patients themselves request to withdraw the trial.

When a patient drops out, the investigators must fill in the reasons for dropout in the case report form, try their best to contact the patient, and complete as much of evaluation items and related examinations. The investigators should fill in the pathography in the last time the patient is contacted, including the patient's last medication time and efficacy. Those who drop out due to adverse events, whether investigational product-related or not, should be recorded in the case report form.

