8.2 Efficacy evaluation

Study endpoints

The primary endpoint was pathological complete response (pCR) rate, pCR was defined as the absence of viable tumour cells in the resected primary tumour specimen and all sampled regional lymph nodes (ypT0N0).

Secondary endpoints were 3-year event-free survival rate (defined as the percentage of patients without disease recurrence or progression or death due to any cause after 3-year follow-up), R0 resection rate (defined as the rate of negative margin microscopically), 3-year OS rate (defined as the percentage of patients alive after 3-year follow-up), complication rate, safety, and quality of life. Adverse events (AEs), duration of which collection was from the time the patient signed the informed consent form to 90 days after surgery, were graded according to the National Cancer Institute Common Terminology Criteria for Adverse Events, version 5.0.

Biomarker analysis

Tissue samples or paraffin sections must be provided as a patient was enrolled. Immunohistochemistry was performed to detect the expression of PD-L1 and DNA mis-match repair (MMR) proteins (MSH6, MSH2, MLH1 and PMS2). PD-L1 combined positive score (CPS) was evaluated using PD-L1 IHC 22C3 pharmDx (Agilent Technologies Inc., California, USA), defined as the number of PD-L1 positive cells (tumour cells, lymphocytes, macrophages) as a proportion of the total number of tumour cells multiplied by 100, Positive PD-L1 expression was considered when CPS was 1 or more. Comprehensive genomic profiling was conducted using targeted gene capture-based next-generation sequencing technology. Briefly, for formalin-fixed paraffin-embedded (FFPE) tissues, hematoxylin and eosin staining (H&E staining) was performed, and the stained sections were evaluated by a pathologist to ensure the tumor cells of $\geq 20\%$. DNA was extracted from the tumor tissues of patients using standard methods. A panel of 418 genes was captured and then sequenced through the Illumina NovaSeq6000 platform (Illumina, San Diego, USA) with 2×150 bp paired-end reads. The average of sequencing depth of tumor

tissues was $\geq 1000X$. Genomic alterations including tumor mutation burden (TMB), single nucleotide variants (SNV), short and long insertions and deletions (INDELs), copy number variants (CNV), and gene fusions were assessed.

Statistical analysis

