According to the previous studies, the pCR rate after preoperative CRT in patients with LARC is approximately 15%. We expected that the regimen of SCRT combined with subsequent chemotherapy and camrelizumab could increase the pCR rate from 15% to 40%. A sample size of 24 patients was required to provide at least 80% power to detect this estimated improvement, in one-sided χ^2 -test with a significance level of 2.5%, and a 20% dropout was considered, resulting in that a total sample size of 30 patients was planned for this study.

Statistical analyses were conducted using SAS® software (version 9.2, SAS Institute Inc, Cary, USA). Continuous variables were summarized using medians and ranges, and categorical variables were described using the frequency and percentage. Baseline and safety analyses were performed for all enrolled patients (intention-to-treat [ITT] population), and efficacy analyses were conducted for those who administrated at least 1 dose of camrelizumab (full analysis set [FAS] population). P value of less than 0.05 was considered statistically significant.

The exploratory objective is: to evaluate the relation of biomarkers (e.g. PD-L1 and MSI) in tumor tissues and/or blood to PD1 efficacy and pCR. Biomarker detection will be carried out with the treated tissue and/or blood obtained prior to treatment.

Continuous variables that conform to normal distribution will be expressed as mean +/- standard deviation, minimum value and maximum value, and those do not conform to normal distribution will be expressed as median; categorical variables will be described in frequency and percentage, and 95% confidence interval will be calculated if necessary. Mean values between the two groups will be compared by t test, and the rates between the two groups will be compared by chi-square test. Survival analysis will be performed by the Kaplan-Meier method. Comparison between groups will be performed by bilateral log-rank test. All tests are two-sided, and 0.05 is taken as the level of the tests.

9. Adverse Event Monitoring

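### The carry-forward rule for a missing primary endpoint cannot be applied to pCR, which is read once on the resected specimen, so the handling of dosed but unresected patients is left open

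*Protocol*

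**What the plan says.** Protocol section 8.2 defines pCR as "absence of viable tumour cells in the resected primary tumour specimen and all sampled regional lymph nodes (ypT0N0"). Section 8.2 also fixes the population: "efficacy analyses were conducted for those who administrated at least 1 dose of camrelizumab (full analysis set [FAS] population"). Section 11.1 repeats that the FAS "includes those who were administrated at least one dose of camrelizumab", and adds the missing-data rule: "When a primary efficacy indicator is missing, the previous result should be carried forward according to the principle of an intention to treat analysis".

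Two places produce efficacy information before or without surgery. The synopsis (dose design and treatment regimen) states: "One week after the completion of neoadjuvant therapy, a second evaluation on the primary lesions will be performed". Section 4.4 has the investigator record details at last contact when a patient drops out, "including the patient's last medication time and efficacy".

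Section 11.2 names overall response rate as the primary efficacy indicator, whereas the synopsis and section 8.2 name pCR. Nothing in the protocol says that a missing pCR in the FAS counts as non-pCR. The nearest rule, in section 11.1, treats patients who drop out for worsening disease after half of the treatment course as failures, but only in the per-protocol set.

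**The concern.** Carrying a previous result forward presupposes a repeated measurement. ypT0N0 is observed at one time, on tissue that exists only after resection, so the rule has nothing to act on. It is still the only rule given for the primary endpoint in the efficacy population, and that population keeps patients who were dosed and never resected.

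An analyst who tries to apply it has three options:

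- carry the baseline state (tumour present), which gives non-pCR;
- find nothing to carry, and leave the patient missing;
- take the last response-type result, which puts a clinical or imaging finding into a pathological endpoint.

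In a 30-patient trial with one primary endpoint, the choice can decide whether the result passes, and the protocol allows it to be made after the data are seen. The label in section 11.2 makes the third option easier to reach, because a pre-surgery response is a natural previous result for an overall response rate.

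**Working it through.** **Inputs from the protocol.** Null rate 15%, target rate 40%, one-sided level 0.025, power at least 80%, 24 evaluable patients, 20% dropout, 30 enrolled (synopsis and section 8.2).

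**Assumptions not in the protocol.** All 30 patients are in the FAS; m of them have no specimen; success is judged by an exact binomial test; under the third option, a carried-forward result is favourable with probability c.

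**1. The plan's own figures.** With n = 24 and success at 8 or more pCRs:

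- P(Bin(24, 0.15) ≥ 8) = 0.0199
- P(Bin(24, 0.40) ≥ 8) = 0.808
- 24 / (1 − 0.20) = 30

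Both 24 and 30 reproduce. The missing-data rule plays no part in them.

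**2. Exact cut at 30 patients.**

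- P(Bin(30, 0.15) ≥ 9) = 0.0278, above 0.025
- P(Bin(30, 0.15) ≥ 10) = 0.0097, so the cut is 10 of 30
- P(Bin(30, 0.40) ≥ 10) = 0.824, the power with nothing missing

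**3. Pre-surgery response carried forward, every carried value favourable (c = 1).** The false-success probability is P(Bin(30 − m, 0.15) ≥ 10 − m).

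| Carried-forward successes m | False-success probability |
|---|---|
| 0 | 0.0097 |
| 1 | 0.022 |
| 2 | 0.049 |
| 3 | 0.099 |

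**4. Same reading at the planned 20% (m = 6), with c varied.** The probability is P(Bin(24, 0.15) + Bin(6, c) ≥ 10).

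| c | False-success probability |
|---|---|
| 0.15 | 0.0097 |
| 0.25 | 0.022 |
| 0.27 | 0.025 |
| 0.30 | 0.031 |
| 0.50 | 0.090 |
| 1.00 | 0.495 |

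The planned level is passed at about c = 0.27. At c = 0.15 there is no inflation.

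**5. Missing counted as non-pCR (c = 0), same cut of 10 of 30.** The probability is P(Bin(30 − m, p) ≥ 10).

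| m | Error at 15% | Power at 40% |
|---|---|---|
| 0 | 0.0097 | 0.824 |
| 1 | 0.0074 | 0.785 |
| 3 | 0.0042 | 0.691 |
| 6 | 0.0015 | 0.511 |

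This handling is safe for the error rate but costs power. The step 24/0.8 = 30 lets dropouts leave the denominator, whereas the FAS keeps every dosed patient.

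**The case against.** A reader might infer that under the stated rule unoperated good responders become pCRs. The protocol does not say so. Section 8.2 ties pCR to resected tissue, so a clinical or imaging response cannot meet the definition. The pathological finding every patient does have beforehand is the diagnostic histology, which shows tumour; carrying that forward gives non-pCR, the same outcome as the repair proposed here. The protocol plans resection for all, has no non-operative pathway, does not define clinical complete response, and gives no response categories for the second evaluation. Of the withdrawal reasons in section 4.4, adverse events and lack of efficacy do not suggest a favourable earlier result. A reader might also infer that the 15% benchmark comes from resected patients only; the protocol does not give its denominator.

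The figures also depend on choices. One carried success leaves the error at 0.022, under 0.025, and c = 0.15 gives none of the inflation. Section 8.2 names a one-sided chi-square test, not an exact one. Without continuity correction, 9 of 30 passes: z = (0.30 − 0.15) / √(0.15 × 0.85 / 30) = 2.30, p = 0.011. The true error at that cut is 0.028 with nothing carried forward.

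All of this stands and limits the size of the claim. It does not rescue the rule. The rule does not fit the endpoint, the protocol itself allows for 20% dropout, and nothing in the text excludes the anti-conservative reading. Nor is this a detail left to the statistical analysis plan: the protocol states a rule, and section 13 requires that plan to follow the protocol.

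**Conclusion.** The point holds in this form: the carry-forward sentence in section 11.1 is wrong for pCR as defined in section 8.2, and it leaves the primary analysis of dosed but unresected patients undetermined. This needs no assumption; it follows from the two sections read together.

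The size of the consequence is conditional. If a pre-surgery response were carried forward, the error rate could exceed 0.025: with two or more carried successes, or, with 6 of 30 missing, once about 27% of them carry a favourable result. These figures assume the exact cut of 10 of 30 and an invented number or rate of favourable carried values. They illustrate what the ambiguity permits and do not predict what the trial will do. Under the other two readings no unresected patient is counted as a pCR on the strength of a clinical or imaging response.

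**What to change.** In section 11.1, delete the carry-forward sentence. State instead that any FAS patient without a resected specimen evaluable for ypT0N0, for any reason, is counted as not having pCR in the primary analysis, and that no value is carried forward. Add a sensitivity analysis restricted to resected patients. Align the primary indicator named in section 11.2 with pCR, so that no other response measure can be taken as the previous result.

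The text change is small, but it has two costs. The reported pCR rate may be lower. The power statement in the synopsis and section 8.2 must also be restated, because dropouts no longer leave the denominator: if 6 of 30 dosed patients have no specimen, power at 40% is about 0.51 instead of 0.82. The sponsor should either state the power for the number of unresected patients it expects or revisit the sample size.

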4.3 Removal criteria

Subjects who do not meet the inclusion criteria but are enrolled should be rejected, including: (1) misdiagnosis; (2) mistaken enrollment; (3) having not taken the medication; (4) having no evaluation records.

The reason of rejection should be explained for all rejected subjects, and their medical history in the study should be reserved for future reference. However, subjects who have received at least one treatment and have at least one safety record can be included in the safety analysis.

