5.5 Concomitant medications

(1) During the clinical trial, except systemic intravenous chemotherapy according to the protocol, patients should stop using other drugs related to systemic treatment of tumor, including other chemotherapy drugs, targeted therapy, immunomodulators, Chinese patent medicine and other drugs that affect the efficacy;

(2) If there is a definite infection, or if the body temperature $\geq 38^{\circ}\text{C}$ and infectious fever cannot be excluded, antibiotics can be used and recorded in the CRF. The use of antifungal or antiviral drugs should also be recorded in the CRF.

(3) The subjects who receive concomitant medications that cause the difficulty of correct judgment of efficacy and safety should be treated as rejected subjects.

6. Medical Ethics Requirements

(1) The clinical trial protocol shall be approved by the ethics committee of the participating institution before it can be implemented. The approval document of the ethics committee on the clinical trial protocol will be copied to each clinical trial institution for the record.

(2) Informed consent form: The investigator should explain the objectives and process of the study to the enrolled subjects, and the informed consent form will be signed after obtaining the consent of the subjects.

This clinical trial will be conducted in accordance with the Declaration of Helsinki (2013 edition) and relevant Chinese Good Clinical Practice. The protocol should be reviewed and approved by the ethics committee of the hospital before the start of the trial. Any necessary modifications to the trial protocol during the clinical study should be reported to the ethics committee for the record.

7. Outcome Measures and Laboratory Tests

7.1 Medical history and physical examination:

Patients should be inquired by the doctor about their present and previous medical history in detail (including histories of allergy, cardiovascular disease, endocrine disease, respiratory system disease, and medication) before

being enrolled in the study. Systematic physical examinations and related laboratory tests will be performed before the trial and after the end of treatment. The medical history, physical examinations and laboratory tests results will be recorded in the CRF.

7.2 Laboratory Tests:

The enrolled patients will receive the following tests before treatment and after the end of the trial:

- 1) Blood routine test (HB + RBC + WBC), and coagulation function test;

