9.2 Criteria for determining adverse event (AE) severity

- 1) Mild: Complain of discomfort, and not requiring symptomatic treatment or drug discontinuance;
- 2) Moderate: Complain of discomfort, requiring symptomatic treatment, not requiring drug discontinuance but requiring reduction of the drug dose by 25%;
- 3) Severe: Complain of significant discomfort, requiring symptomatic treatment and drug discontinuance.

9.3 Criteria for determining the relationship between adverse event (AE) and the investigational product

According to the criteria for determining the causality between the drug and AEs, the correlation between AEs and the investigational product is divided into five grades: definitely related, probably related, possibly related, possibly unrelated, and definitely unrelated. The three conditions of definitely related, probably related, and possibly related are classified as adverse reactions caused by the investigational product. The total number of subjects with investigational product-related adverse reactions is taken as the numerator, and the number of all enrolled subjects for adverse reaction evaluation is taken as the denominator to calculate the incidence rate of adverse reaction. Please refer to Table 2 for specific determination.

Clinical Study Protocol

Version No.: V2.0

Table 2. Criteria for determining the causality of adverse drug reactions

Indicator	Definitely related	Probably related	Possibly related	Possibly unrelated	Definitely unrelated
Reasonable chronological sequence	Yes	Yes	Yes	Yes	No
Conforming to the known reaction type of the investigational product	Yes	Yes	Yes	No	No
Improving after the discontinuance of the investigational product	Yes	Yes	Yes or No	Yes or No	No
Recurring after reusing the investigational product	Yes	?	?	?	No
Possible other explanation for the drug-induced reaction	No	No	Yes	Yes	Yes

Note: ? means that the medicine is not allowed to be administrated again due to medical ethics. "Possibly unrelated" indicates that further observation is needed for evaluation.

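### The protocol gives conflicting safety populations, and the safety set lets treated patients be left out after exposure by a judgment with no stated criterion

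*Protocol*

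**What the plan says.** Four places in the protocol say who counts for safety.

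- **8.2, Statistical analysis:** "Baseline and safety analyses were performed for all enrolled patients (intention-to-treat [ITT] population"). Treatment is not required and nobody is excluded.
- **11.1, Safety set:** the SS is "subjects who have received at least one treatment and have actual safety assessment data". Some rejected but evaluable subjects may enter, "excluding those who cannot be evaluated for safety due to the use of prohibited drugs". The section then fixes the denominator: "The number of subjects in the SS will be used as the denominator for the incidence of ARs".
- **9.3, Relationship to the investigational product:** "the number of all enrolled subjects for adverse reaction evaluation is taken as the denominator to calculate the incidence rate of adverse reaction".
- **4.3, Removal criteria:** after listing grounds for rejection, it allows that "subjects who have received at least one treatment and have at least one safety record can be included in the safety analysis". It has no prohibited-drug exclusion.

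Section 5.5 bears on the exclusion. Item (1) tells patients to stop other drugs for systemic tumour treatment, a list that runs on to "immunomodulators, Chinese patent medicine and other drugs that affect the efficacy". Item (3) makes a subject a rejected subject if concomitant medication makes efficacy and safety hard to judge correctly.

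**The concern.** There are two faults. First, the protocol does not settle which patients form the denominator of the safety tables. The rule in 8.2 and the rule in 11.1 give different answers as soon as one enrolled patient goes untreated or one treated patient is excluded.

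Second, the exclusion in 11.1 is applied after treatment has begun, to patients who may already have recorded adverse events. The protocol gives no criterion for being unevaluable for safety, and in a single-arm trial the judgment can be made with the events in view. A confounding drug may make an event harder to attribute, but that does not justify removing the exposed patient. Section 9.3 already grades causality in five levels, with a row for alternative explanations.

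Safety is the secondary objective (section 2) and 30 patients are planned, so moving one or two patients visibly changes a reported rate.

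**Working it through.** **Base number.** Section 8.2 requires 24 patients and allows 20% dropout: 24/(1 − 0.20) = 30. This reproduces the planned 30, and the figure is not in dispute.

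**The rules side by side.**

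| Section | Treatment required | Safety data required | Prohibited-drug exclusion |
|---|---|---|---|
| 8.2 | no | no | no |
| 11.1 (SS) | yes | yes | yes, if judged unevaluable |
| 9.3 | unclear | unclear | not stated |
| 4.3 (rejected subjects) | yes | yes, one record | no |

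The clear contradiction is 8.2 against 11.1. The two agree only if every enrolled patient is treated, has safety data and is retained. For a rejected, treated patient with a safety record, 4.3 permits inclusion, while 11.1 excludes the patient if prohibited drugs are held to prevent evaluation.

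**Effect of the exclusion.** Let n be the treated patients, x those with the event, a the excluded patients with the event, and b the excluded patients without it. The reported rate is

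(x − a)/(n − a − b).

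It falls below x/n when a/(a + b) > x/n, that is, when events are commoner among those removed than among all treated patients. It rises when the inequality is reversed.

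The protocol gives no event rate, so the counts below are assumptions. All 30 patients are taken as treated.

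| True rate | Excluded | Reported rate |
|---|---|---|
| 10/30 = 33.3% | none | 10/30 = 33.3% |
| 10/30 = 33.3% | 2 event-free | 10/28 = 35.7% |
| 10/30 = 33.3% | 2 with event | 8/28 = 28.6% |
| 10/30 = 33.3% | 4 with event | 6/26 = 23.1% |
| 3/30 = 10.0% (95% CI 2.1 to 26.5) | 3 with event | 0/27 = 0% (0 to 12.8) |
| 1/30 = 3.3% (0.1 to 17.2) | 1 with event | 0/29 = 0% (0 to 11.9) |

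The intervals are Clopper-Pearson. The rows in which every excluded patient had the event are the unfavourable end of the range. For a rare serious event, one exclusion can remove it from the table.

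**Effect of counting untreated patients.** Suppose 6 patients have an adverse reaction and 30 are enrolled. The all-enrolled rate in 8.2 is 6/30 = 20.0%. If only 27 were treated, the rate among the treated is 6/27 = 22.2%. If only 24 were treated (the whole 20% allowance of 6 untreated, an extreme case), it is 6/24 = 25.0%. Untreated patients therefore lower the rate, which is the same direction as excluding patients with events.

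**The case against.** The strongest reply is that the text is narrower than it looks, and much of that reply stands.

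- A reader might infer that the SS drops everyone who took a prohibited drug. It does not. The clause sits in a sentence about rejected subjects and removes only those who cannot be evaluated for safety for that reason. What remains is that nothing defines that condition.
- A reader might infer that patients given immunosuppressive treatment for immune-related toxicity are removed. The documents do not say so. Item (1) of 5.5 lists immunomodulators among tumour treatments. Corticosteroids and immunosuppressants are restricted by name only in the eligibility criteria, for the two weeks before study drug. Section 5.4 expects immune-related events and asks that appropriate medications be ready. Removal would need two discretionary steps: rejection under 5.5(3), then a finding of unevaluable. It is possible, because no passage exempts such patients, but it is only an example of what the wording allows.
- A reader might count 9.3 as a further conflicting denominator. Its phrase can mean enrolled subjects who were evaluated for adverse reactions, which is close to the SS. It is ambiguous rather than contradictory.
- Section 4.3 lessens the harm by letting treated, rejected subjects in. It does so permissively and without reference to the exclusion in 11.1, so it adds another rule to reconcile.
- Section 8.2 collects adverse events from consent, which gives all-enrolled reporting some rationale. A separate listing of pre-treatment events meets that need.

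Leaving the matter to a statistical analysis plan is not enough. Section 13 has that plan written according to the protocol, so it would inherit two incompatible instructions.

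**Conclusion.** The point holds on two counts: 8.2 and 11.1 name different safety populations, and 11.1 contains an undefined exclusion applied after exposure. The conflict follows from the text alone. Its practical size depends on how many patients are untreated or excluded, and it is zero if there are none.

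The direction of bias is not fixed. On the assumed 10/30, excluding two patients moves the reported rate from 33.3% to 28.6% if both had the event, or to 35.7% if neither did. A claim that the rate must be understated would need evidence that excluded patients have events more often than those kept, and the documents give none. The pCR analysis is not affected. The change should be made, because safety is a stated objective and the safety tables cannot be produced unambiguously as the protocol stands.

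**What to change.** Define one safety set: all patients who received any part of study treatment (radiotherapy, chemotherapy or camrelizumab), with no exclusion for concomitant or prohibited medication. Then:

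- **11.1:** adopt this definition and delete the prohibited-drug exclusion.
- **8.2:** replace all enrolled patients with the safety set for safety analyses.
- **9.3:** name the safety set as the adverse reaction denominator.
- **4.3:** state that rejected subjects who received any study treatment belong to the safety set.
- **5.5(3):** add that rejection does not remove a treated patient from the safety set.

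List prohibited-drug use as a protocol deviation and flag events that follow it. List adverse events between consent and first treatment separately.

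The cost is wording in five sections. It needs no new data and no change to patient care.
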